6.3 Secondary Endpoints

6.3.1 Pharmacokinetics

PK blood samples will be collected post-infusion at 1, 3, 5, 10, 30, and 60 minutes (+/- 1 minute), and 4, 8, and 24 hours (+/- 5 minutes).

6.3.2 Bio-distribution / Tumoral Penetration

A fresh tumor sample will be collected at the time of the patient's tumor resection surgery. It will be assayed with Inductively Coupled Plasma Mass Spectrometry (ICP-MS) to determine accumulated dose.

6.3.3 Feasibility

To assess feasibility, the rate of successful production, delivery, and administration of the investigational product and subsequent resection will be calculated.

6.4 Exploratory Endpoints

6.4.1 Bcl2L12 and apoptotic marker expression levels

An exploratory objective will assess for Bcl2L12 levels in tumor tissue collected post administration of NU-0129 using IHC/IF as well as RT-qPCR. Other apoptotic markers will be analyzed as well using IHC.

6.4.2 Preliminary Response

will be measured by Overall Survival and Progression Free Survival at 6 months post treatment as well as Overall Response Rate. Brain MRI's will be performed at least every 12 weeks during follow-up.

7.0 ADVERSE EVENTS

This study will be conducted in compliance with the study-specific standard operating procedure (SOP) and per the DSMP guidelines of the Robert H. Lurie Comprehensive Cancer Center of Northwestern University for in-house research. The level of risk attributed to this study requires High Risk Monitoring as outlined in the [SOP](#). In addition, the study will abide by all safety reporting regulations, as set forth in the Code of Federal Regulations.

7.1 Adverse Event Monitoring

Adverse event data collection and reporting, which are required as part of every clinical trial, are done to ensure the safety of subjects enrolled in the studies as well as those who will enroll in future studies using similar agents. Adverse events are reported in a routine manner at scheduled times during a trial (see Section 5 for time points). In addition, certain adverse events must be reported in an expedited manner to allow for optimal monitoring and patient safety and care.

All patients experiencing an adverse event, regardless of its relationship to study drug, will be followed until:

- the adverse event resolves or the symptoms or signs that constitute the adverse event return to baseline;
- any abnormal laboratory values have returned to baseline;
- there is a satisfactory explanation other than the study drug for the changes observed; or
- death.

7.2 Definitions & Descriptions

7.2.1 Adverse Event

An adverse event (AE) is any untoward medical occurrence in a patient receiving study treatment and which does not necessarily have a causal relationship with this treatment. An AE can therefore be any unfavorable and unintended sign (including an abnormal laboratory finding), symptom, or disease temporally associated with the use of an experimental intervention, whether or not related to the intervention.

Recording of AEs should be done in a concise manner using standard, acceptable medical terms. In general, AEs are not procedures or measurements, but should reflect the reason for the procedure or the diagnosis based on the abnormal measurement. Preexisting conditions that worsen in severity or frequency during the study should also be recorded (a preexisting condition that does not worsen is not an AE). Further, a procedure or surgery is not an AE; rather, the event leading to the procedure or surgery is considered an AE.

If a specific medical diagnosis has been made, that diagnosis or syndrome should be recorded as the AE whenever possible. However, a complete description of the signs, symptoms and investigations which led to the diagnosis should be provided. For example, if clinically significant elevations of liver function tests are known to be secondary to hepatitis, "hepatitis" and not "elevated liver function tests" should be recorded. If the cause is not known, the abnormal test or finding should be recorded as an AE, using appropriate medical terminology (e.g/ thrombocytopenia, peripheral edema, QT prolongation).

7.2.2 Severity of AEs

All adverse events will be graded according to the NCI Common Terminology Criteria for Adverse Events (CTCAE) version 4.03. The CTCAE v4.03 is available at <http://ctep.cancer.gov/reporting/ctc.html>

If no CTCAE grading is available, the severity of an AE is graded as follows:

- Mild (grade 1): the event causes discomfort without disruption of normal daily activities.
- Moderate (grade 2): the event causes discomfort that affects normal daily activities.
- Severe (grade 3): the event makes the patient unable to perform normal daily activities or significantly affects his/her clinical status.
- Life-threatening (grade 4): the patient was at risk of death at the time of the event.
- Fatal (grade 5): the event caused death.

7.2.3 Serious Adverse Events (SAEs)

All SAEs, regardless of attribution, occurring from time of signed informed consent, through 21 days after the administration of study drug, must be reported upon discovery or occurrence.

An SAE is defined in regulatory terminology as any untoward medical occurrence that:

- Results in *death*.
If death results from (progression of) the disease, the disease should be reported as event (SAE) itself.
- Is life-threatening.
The patient was at risk of death at the time of the event; it does not refer to an event that hypothetically might have caused death if it were more severe.
- Requires in-patient hospitalization or prolongation of existing hospitalization for ≥ 24 hours.
- Results in persistent or significant disability or incapacity.
- Is a congenital anomaly/birth defect.
- Is an important medical event.

Any event that does not meet the above criteria, but that in the judgment of the investigator jeopardizes the patient, may be considered for reporting as a serious adverse event. The event may require medical or surgical intervention to prevent one of the outcomes listed in the definition of "Serious Adverse Event".

For example: allergic bronchospasm requiring intensive treatment in an emergency room or at home; convulsions that may not result in hospitalization; development of drug abuse or drug dependency.

7.2.4 Unanticipated Problems Involving Risks to Subject or Others

A UPIRSO is a type of SAE that includes events that meet ALL of the following criteria:

- Is *unanticipated* in terms of nature, severity, or frequency
- Places the research subject or others at a different or *greater risk of harm*
- Is deemed to be *at least possibly related* to participation in the study.

7.3 Adverse Event Reporting

7.3.1 Routine Reporting

All routine adverse events, such as those that are expected, or are unlikely or definitely not related to study participation, are to be reported on the appropriate eCRF. Routine AEs will be reviewed by the external Data Safety Monitoring Board (DSMB) according to the study's phase and risk level, as outlined in the DSMP. NU's Data Monitoring Committee (DMC) will also be informed.

7.3.2 Determining if Expedited Reporting is Required

This includes all events that occur within 30 days of the last dose of protocol treatment. Any event that occurs more than 30 days after the last dose of treatment and is attributed (possibly, probably, or definitely) to the agent(s) must also be reported accordingly.

- 1) Identify the type of adverse event using the NCI CTCAE v 4.03.
- 2) Grade the adverse event using the NCI CTCAE v 4.03.
- 3) Determine whether the adverse event is related to the protocol therapy.

Attribution categories are as follows:

- Definite: AE is clearly related to the study treatment.
- Probable: AE is likely related to the study treatment.
- Possible: AE may be related to the study treatment.
- Unlikely: AE not likely to be related to the study treatment.
- Unrelated: AE is clearly NOT related to the study treatment.

- 4) Determine the prior experience of the adverse event.

Expected events are those that have been previously identified as resulting from administration of the agent. An adverse event is considered unexpected, for expedited reporting purposes only, when either the type of event or the severity of the event is not listed in:

- the current protocol
- the drug package insert
- the current Investigator's Brochure

7.3.3 Expedited Reporting of SAEs/Other Events

7.3.3.1 Reporting to the external DSMB

All SAEs must be reported to the DSMB within 24 hours of becoming aware of the event. The study coordinator must complete the Medwatch and NU SAE Forms, provided as a separate documents, and submit to the appropriate QAM at [contact]. The QAM will distribute to the DSMB appropriately.

The completed form should assess whether or not the event qualifies as a UPIRSO. The report should also include:

- Protocol description and number(s)
- The patient's identification number
- A description of the event, severity, treatment, and outcome (if known)
- Supportive laboratory results and diagnostics
- The hospital discharge summary (if available/applicable)

All SAEs will be reported to, and reviewed by, the external DSMB within 24 hours, and will also be reviewed by the NU DMC at their next meeting.

7.3.3.2 Reporting to the Northwestern University IRB

The following information pertains to the responsibilities of the lead site (Northwestern University). Additional participating sites should follow their local IRB guidelines for reporting to their local IRBs.

- Any death of an NU subject that is unanticipated in nature and at least possibly related to study participation will be promptly reported to the NU IRB within 24 hours of notification.
- Any death of an NU subject that is actively on study treatment (regardless of whether or not the event is possibly related to study treatment)

- Any death of a non-NU subject that is unanticipated and at least possibly related and any other UPIRSOs will be reported to the NU IRB within 5 working days of notification.
- All other deaths of NU subjects not previously reported, other non-NU subject deaths that were unanticipated and unrelated, and any other SAEs that were not previously reported as UPIRSOs will be reported to the NU IRB at the time of annual continuing review.

7.3.3.3 Reporting to the FDA

The FDA will be notified within 7 calendar days of any SAE that is associated with study treatment, is unexpected, and is fatal or life-threatening.

The FDA will be notified within 15 calendar days of any SAE that is associated with the study treatment, unexpected, and serious but *not fatal or life-threatening*. This includes any previous SAEs that were not initially deemed reportable, but are later determined to meet the criteria for reporting (i.e. by the DMC).

All other SAEs will be reported on an annual basis as part of the annual FDA report.

8.0 DRUG INFORMATION

8.1 Agent NU-0129

8.1.1 Other names
n/a

8.1.2 Classification - type of agent
Bcl2L12-targeting Spherical Nucleic Acid (SNA)

8.1.3 Mode of action

NU-0129 is spherical nucleic acid (SNA) designed to target the silencing of Bcl2L12 gene expression, an overexpressed protein that plays an important role in driving the pathogenesis of glioblastoma multiforme (GBM) and mediating therapeutic resistance. SNAs are three dimensional conjugates consisting of densely functionalized and highly oriented nucleic acids covalently attached to the surface of nanoparticles. NU-0129 is composed of 13nm gold nanoparticles surrounded by siRNAs tailored to recognize Bcl2L12 sequence.

8.1.4 Storage and stability

NU-0129 in powder form should be at -20°C ($\pm 5^{\circ}\text{C}$) freezer. Once prepared in liquid/solution form, if not used immediately, NU-0129 could be stored up to 8 hours in room temperature (20-25 °C). Remaining or unused solution should be stored at 4°C. Solution must NOT be frozen.

8.1.5 Protocol dose specifics

Each patient's dose will be based on his or her weight at screening. Patients will be dosed based on total body weight and the resulting dose will be rounded to one of the 5 dose groups as shown in dosing chart below. Nominal dose will be 0.04mg/kg (approximately 0.03 to 0.05 mg/kg).

Patient's weight in kg	Dose in mg (Oligonucleotide component)	Corresponding dose (mg/kg)
Up to 37.0 kg	0.987 mg	Up to 0.027
≥ 37.0 to < 61.7 kg	1.974 mg	0.053 to 0.032

≥ 61.7 to < 86.4 kg	2.96 mg	0.048 to 0.034
≥ 86.4 to < 111.0 kg	3.95 mg	0.046 to 0.036
≥ 111.0 to 135.7 kg	4.94 mg	0.045 to 0.036

8.1.6 Preparation. Refer to pharmacy manual for complete study drug preparation procedures.

- Prior to reconstitution, the vials should be equilibrated to room temperature to reach room temperature for 5-30 minutes. .
- Vials can be stored at room temperature (20-25 °C) for up to 3 hours. This includes thawing time and reconstitution time.
- Vials should not be refrozen after thawing.
- Each NU-0129 manufactured clinical vial should be reconstituted in 1mL SWFI for final concentration approximately 0.987 mg/ml.
- Mix the solution in the vial by gentle swirling or gentle shaking by benchtop sonicator, if available.
- Visually inspect for particulate matter and discoloration prior to administration. Reconstituted solution should red or maroon color, free of visible particles.
- Calculate the dose and the amount of vials required based on the dosing chart.
- Withdraw the full content of the NU-0129 vials and inject into an appropriate size bag of normal saline (0.9% sodium chloride).
- Reconstituted solution should be further diluted with normal saline (0.9% sodium chloride) to 1:50 dilution.
- Preparation should take place immediately prior to administration, but, if needed, reconstituted vials and/or IV bags may be stored at room temperature (20-25 °C) for up to 8 hours (including administration time).
- Administer study drug using non-PVC/DEHP administration set with a sterile, non-pyrogenic, low-protein binding 0.22 µm filter.
- Visually inspect final product for particulate matter and discoloration prior to administration. Do not use and discard the drug product vial if extraneous particulate matter is observed.

8.1.7 Route of administration for this study
Intravenous

8.1.8 Incompatibilities

Given unknown compatibility data with PVC/DEHP materials, PVC/DEHP-free bags and administration set should be used for drug preparation. Refer to pharmacy manual for a full list of materials acceptable and required.

8.1.9 Availability & Supply

NU-0129 is an investigational product, which will be manufactured and supplied by University of Iowa Pharmaceuticals. The drug product is supplied as approximately 0.987mg per vial lyophilized powder to be reconstituted with SWFI and further diluted with 0.9% sodium chloride by pharmacy on the day of administration. .

8.1.10 Side effects

As this is a first-in-human trial, side effects in this population are not completely known. In the primate and non-primate treatment trials, a few noted side effects were observed. Gold nanoparticle accumulation in the liver has occurred in some pre-clinical studies as well as skin discoloration following the infusion have been seen with animal models displaying a purple hue to their baseline skin

tone. Hypercholesterolemia was also observed in the non-primate model (rat model).

Possible side effects:

Liver Damage
Skin Discoloration
Infusion Reaction
Hypercholesterolemia
Low blood pressure

There is no significant toxicity associated with the chemistry or manufacturing of the drug product.

8.1.11 Nursing implications

The dose (based on dosing chart) will be based on the patient's weight at baseline. The infusion rate will be 5.0-8.0 mL/minute. A sterile, non-pyrogenic, low-protein binding 0.22 μ m in-line filter must be used during administration to remove any adventitious particles. If the infusion set does not contain in-line filter, 0.22 μ m add-on filter should be used. The flow rate will be monitored closely and the tissue surrounding the catheter examined frequently for any signs of extravasation.

Drug Administration Log should be completed by administering nurse and returned to study coordinator, documenting date and time of infusion start/ stop, interruptions (if any). Any staining or discoloration of the syringe, IV bag, delivery device, and /or administration set should be documented in the Administration Log.

8.1.12 Return and Retention of Study Drug

Drug accountability records will be maintained for all clinical trial supplies. Remaining or unused solution should be stored at 4°C. Refer to pharmacy manual for management of all unused clinical trial supplies. .

9.0 CORRELATIVES/SPECIAL STUDIES

All patients must provide blood samples for pharmacokinetic analysis as well as tumor tissue during their surgery to assess accumulated dose, expression of Bcl2L12 levels, and other apoptotic markers. Archival tissue will be collected at baseline if available.

9.1 Blood Sample Collection Guidelines

Blood samples will be collected for PK analysis at 1, 3, 5, 10, 30, and 60 minutes (\pm 1 minute), and 4 hours, 8 hours, and 24 hours (\pm 5 minutes) post NU-0129 infusion. Each sample will contain 1mL of blood collected in pre-chilled 4mL K2EDTA tubes and maintained on wet ice throughout collection and processing. See separate lab manual for full collection and processing details.

9.2 Fresh tumor samples

Patients will undergo a tumor resection 8-48 hours after treatment with NU-0129. The mass that is removed during surgery will be collected and processed for the study as detailed in section 9.4.2 below.

9.3 Archival tissue

All patients must provide an archival tissue sample if it is available. This tissue will undergo histology testing for Bcl2L12 and other apoptotic markers as indicated in section 9.4.2.1.

9.4 Sample Processing, Storage, and Shipment

9.4.1 Pharmacokinetic Blood Samples

PK blood samples should be drawn into pre-chilled 4mL K2EDTA tubes and must be immediately chilled on ice and transported to PCF-CTU (Pathcore Facility Clinical Trials Unit). Samples will be spun down within 15 minutes of collection in a temperature-controlled (4°C) centrifuge. Samples should be immediately flash-frozen on dry ice and stored frozen (-65°C to -85°C). The plasma samples will be shipped on dry ice to Covance. See separate lab manual for shipping instructions.

Note: While the patient's tumor resection surgery should ideally be planned around the timing of PK blood draws, it is acceptable for blood draws to take place during surgery. Such cases should be planned closely with the surgical team.

9.4.2 Tissue

All patients will undergo a tissue resection 8-48 hours after NU-0129 administration. The full tissue sample will be sent for pathology processing and samples will be processed and shipped for the study as described below.

In addition, patients will provide an archival tissue sample at screening if it is available. 10 unstained slides will be processed for histological testing as in section 9.4.2.1.

9.4.2.1 Histology (apoptotic markers e.g. caspase)

For both archival and fresh tissue samples, 10 unstained slides will be requested for Bcl2L12 Immunohistochemistry (IHC), Immunofluorescence (IF), TUNEL (Terminal deoxynucleotidyl transferase), and active caspase-3 staining. See separate lab manual for details of processing and analysis.

9.4.2.2 Bcl2L12 expression in tissue (RNA)

A tissue sample (0.5cm x 05cm) will be collected and processed for RNA analysis as detailed in a separate lab manual. Half of the sample will be used for RNA extraction, and the other half will be stored in -80°C for reserve use.

9.4.2.3 Tissue Bio-Distribution

Any remaining tissue (whether necrotic or not) will be processed by PCF-CTU and shipped frozen to QBIC for bio-distribution studies. Please see lab manual for shipping and processing details.

9.5 Assay Methodology

9.5.1 PK blood samples

See lab manual for details on PK assay methodology.

9.5.2 Tissue – IHC

Tissue samples will be processed for Bcl2L12 IHC, IF, TUNEL, and active caspase-3. See lab manual for details.

9.5.3 Tissue – RNA

Extracted RNA will be frozen and sent to NUSeq Core for RACE analysis.

9.5.4 Tissue – Biodistribution

Remaining tissue will be sent to QBIC for ICP-MS of biodistribution. See lab manual for details.

9.6 Specimen Banking

Any excess tissue should be stored in Northwestern University's biorepository for future unspecified use. Samples will be stored indefinitely until exhausted or the patient withdraws consent for storage.

10.0 STATISTICAL CONSIDERATIONS**10.1 Study Design/Study Endpoints**

This is a single group Phase 0 study. A small number n=6-8 of patients will be given the treatment and observed for a fixed period of time.

10.2 Sample Size and Accrual

The sample size n=6, 7, or 8 was determined on the basis of feasibility of recruitment and of conducting the study. This is the first study in humans or this treatment, and it was felt that both the primary and secondary outcomes can be estimated with sufficient precision with such n, while few patients would be put to risk.

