2.0 OBJECTIVES & ENDPOINTS

2.1 Primary Objective & Endpoint

- The primary objective is to assess the safety of intravenous NU-0129 in patients with recurrent GBM or GS.
- The total incidence of adverse events will be evaluated using CTCAE v4.03 from the time of informed consent to 21 days after study drug administration. Adverse events will be monitored during and immediately after the infusion as well as weekly for 21 days after treatment administration.

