2.2.3 Feasibility

- To assess the feasibility of giving NU-0129 as a standard treatment for recurrent GBM or GS.
- Feasibility will be calculated as the rate of successful production, delivery, and administration of the investigational product and subsequent resection.

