6.2 Primary Endpoint

Safety will be measured by recording adverse events using CTCAE v4.03 from the time a patient signs consent to 21 days after study drug administration. Any patient who has received at least a partial dose of NU-0129 will be evaluable for this endpoint. If a patient has a continuing adverse event at 21 days which is related to treatment, it will be followed until resolution to baseline or Grade ≤ 2.

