10.3 Data Analyses Plans**10.3.1 Primary Objective**

To evaluate the safety of NU-0129 SNA gold nanoparticle infusion in patients with recurrent GBM or GS, we will count and record the number of adverse events.

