10.3.2 Secondary Objectives

To evaluate the bio-distribution of NU-0129 in tumor tissue we will provide descriptive statistics regarding intensity of concentration of particles in various parts of tumor tissue.

To evaluate the pharmacokinetics of NU-0129 in blood samples collected at 1, 3, 5, 10, 30, 60 minutes and 4, 8, and 24 hours post-dose, we will provide appropriate pharmacokinetic curves and parameters such as Cmax, Tmax etc.

To evaluate the feasibility of NU-0129 administration, we will record a) successes/failures, b) number of attempts to administrate nanoparticles.

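### Section 10.2 claims adequate precision at n=6–8 without a criterion; the limits are very wide, and the raw event count in 10.3.1 does not estimate adverse event incidence

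*Combined protocol and SAP*

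**What the plan says.** Section 10.1 describes the design: "This is a single group Phase 0 study". Section 10.2 gives the reason for its size: "The sample size n=6, 7, or 8 was determined on the basis of feasibility of recruitment and of conducting the study". The next sentence adds a separate statistical statement, that "it was felt that both the primary and secondary outcomes can be estimated with sufficient precision with such n", and notes that few patients would be exposed to risk.

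The primary endpoint is in section 2.1: "The total incidence of adverse events will be evaluated using CTCAE v4.03 from the time of informed consent to 21 days after study drug administration". Section 6.2 supplies the safety population: "Any patient who has received at least a partial dose of NU-0129 will be evaluable for this endpoint". The analysis in section 10.3.1 is that "we will count and record the number of adverse events".

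Among the secondary endpoints, section 2.2.3 makes feasibility a proportion: "Feasibility will be calculated as the rate of successful production, delivery, and administration of the investigational product and subsequent resection". For bio-distribution, section 10.3.2 says "we will provide descriptive statistics regarding intensity of concentration of particles in various parts of tumor tissue"; for pharmacokinetics it plans curves and summary parameters. No analysis in section 10 includes a confidence interval.

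**The concern.** The clause in 10.2 is the plan's only statement about precision, and it covers the primary and the secondary outcomes together. Nothing in section 10 says what precision would be enough, or what these numbers of patients deliver. If the clause stays, a report with no drug-related events, or with every patient treated and resected as planned, could cite the protocol as having judged the estimate precise.

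The planned primary analysis adds to the difficulty. A total number of events does not show how many patients were affected, so it cannot be read as a patient-level rate or given a binomial interval. It also has no breakdown by cause. The collection window opens at consent, before dosing, and it contains a craniotomy in every patient who follows the plan. A single total would therefore combine events before the drug, events of surgery and events of the drug.

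**Working it through.** **Inputs.** n = 6, 7 or 8 (section 10.2); safety denominator of patients given at least a partial dose (section 6.2); feasibility as a proportion (section 2.2.3). The plan states no confidence level, so two-sided 95% is assumed here. It also gives no target rate, standard deviation or interval width, so n=6–8 can be neither reproduced nor refuted from the plan's own inputs.

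**Formulas (exact, Clopper–Pearson).**
- No events in n patients: upper limit = 1 − 0.025^(1/n).
- x events in n patients: upper limit = 0.975 quantile of Beta(x+1, n−x).
- n successes in n: lower limit = 0.025^(1/n).

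| Observed | n=6 | n=7 | n=8 |
|---|---|---|---|
| 0 patients with the event, upper limit | 45.9% | 41.0% | 36.9% |
| 1 patient with the event, upper limit | 64.1% | 57.9% | 52.7% |
| All feasibility successes, lower limit | 54.1% | 59.0% | 63.1% |

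Example for the first row, n=6: 1 − 0.025^(1/6) = 1 − 0.541 = 0.459.

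**Sensitivity to the choice of limit, 0/n.** One-sided 95%, 1 − 0.05^(1/n): 39.3%, 34.8%, 31.2%. Wilson two-sided 95%: 39.0%, 35.4%, 32.4%. The reading does not change.

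**Chance of missing an event.** If the true per-patient rate were 10% (an illustrative value), the probability of seeing no case is 0.9^6 = 53% at n=6 and 0.9^8 = 43% at n=8.

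**Continuous secondary outcomes.** For a mean of a roughly normal measure, the 95% half-width is t(0.975, n−1)/√n standard deviations: 1.05 SD (n=6), 0.92 SD (n=7), 0.84 SD (n=8). The plan gives no SD, so this cannot be put in units of concentration.

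**Count against proportion.** Suppose six events are recorded among six dosed patients. They could all be in one patient (1/6, interval 0.4% to 64.1%) or one in each patient (6/6, interval 54.1% to 100%). The count in 10.3.1 is the same in both cases.

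**What falls in the window.** Consent may precede registration by 28 days (Table 5.1, footnote 1) and dosing may follow registration by 14 days (section 4.6). Up to 28 + 14 = 42 days before dosing can therefore contribute events, against 21 days after it. The resection comes 8–48 hours after infusion (section 4.2), inside the 21 days.

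**The case against.** The other side has several fair points. The sample size does not rest on the precision clause: feasibility is the stated reason, which is reasonable for a Phase 0 study, and section 10.1 openly calls the number small. The clause reports a judgment with no criterion attached, so calculation cannot show it to be false. A reader might infer from the limits that 10.2 contains an arithmetic error or that more patients are needed. The documents support neither: the clause is unsupported, not refuted.

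The zero-event limits also do not fit adverse events of any cause. With surgery planned for every patient inside the window, no events at all is implausible. The limits apply to a specific or drug-related event. That narrows the point but does not remove it, because those are the events a first-in-human safety study needs to describe.

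The safety population, CTCAE grade (section 7.2.2) and attribution (section 7.3.2) are all defined. What is missing is the instruction to use them in the analysis. The total in section 2.1 might be read as a plain number of events, but then it still does not say how many patients were affected.

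The plan sets no safety or feasibility threshold. Dosing of further patients rests on DSMB review after each patient and of possibly related Grade 2 or higher events (section 4.3). That protects patients during the trial; it does not make the estimates precise. The risk of over-reading the results is a possibility, not something the plan announces.

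Finally, a reader might turn the one-sided limits into a statement that the trial excludes toxicity rates above about 31%–39%. That holds only if no such event occurs. One event already gives a two-sided upper limit of 53% (1/8) to 64% (1/6).

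**Conclusion.** The precision clause in 10.2 has no support in the plan, and the design delivers only wide limits. If no patient has a given drug-related event, a true rate of up to 37%–46% remains compatible with the data. If every feasibility attempt succeeds, a true success rate as low as 54%–63% remains compatible. The count in 10.3.1 does not estimate the incidence named in 2.1.

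The figures assume a two-sided 95% level, exact limits, independent patients and 6 to 8 patients in the denominator, and each is conditional on the number of events observed. Under section 4.9, a dosed patient without timely surgery still counts for toxicity and another may be added, so the safety denominator may exceed 8. With ten dosed patients, for example, the zero-event upper limit would be 1 − 0.025^(1/10) = 30.8%.

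This is a modest wording and reporting fault. It does not call n into question.

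**What to change.** **Section 10.2.** Keep the feasibility rationale for n. Delete the precision clause and state that the study is descriptive. Give the limits tabulated above for n=6, 7 and 8, labelled as exact two-sided 95% and as conditional on the observed number of events. Do not add an unconditional statement that rates above some value are excluded.

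**Section 10.3.1.** Report the number and proportion of dosed patients with at least one adverse event, by CTCAE grade and by relatedness, with Clopper–Pearson 95% intervals based on the actual number dosed. The event count can remain as a supplement.

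**Section 10.3.2.** Report the feasibility rate with the same kind of interval and state its denominator, since a failure of production or delivery occurs before dosing.

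**Cost.** A protocol amendment with its review (section 11.2), a little more analysis work, and a less favourable precision statement. No patients, visits or samples are added, because grade and attribution are already to be assessed.
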